7.5 Objective Response Rate

The objective response rate is defined as the proportion of patients showing a best overall response of CR or PR during the core study (i.e. up to 12 months) according to RECIST V. 1.1 criteria. For the assessment of SD as best overall response, there is no specific time needed from baseline as the first tumor evaluation takes place after 12 weeks (at Visit 8) from randomization thus conforming the required minimum time of 6 weeks from randomization based on RECIST 1.1 guidelines. Therefore, the best overall response is interpreted as the best response recorded from the start of the treatment until disease progression/recurrence, death from any cause or until the patient withdraws consent, whichever is earliest. In order to have a best overall response of CR or PR, response must be confirmed by another response assessed at least 4 weeks after the initial response. The objective response rate will be calculated at 12 months and displayed with 95 percent exact binomial confidence intervals (implemented using SAS procedure FREQ with EXACT statement for one-way tables) [Clopper & Pearson, 1934]. Frequencies of each response will also be included. This will be carried out for all patients in the full analysis set.

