7.1.4 End of core study visit, including premature withdrawal and study discontinuation visit

Patients who discontinue study treatment should be scheduled for a visit as soon as possible, at which time all of the assessments listed for the end of core study visit/early withdrawn will be performed. Study treatment discontinuation in the pasireotide LAR plus everolimus arm is defined as the withdrawal of both study drugs; the date and reason for stopping the study treatment should be reported in the CRF. At a minimum, all patients who discontinue study treatment, including those who refuse to return for a final visit, will be contacted for safety evaluations 56 days after the last dose of pasireotide LAR or everolimus, whichever comes last.

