7.2.1.1.1 Tumor Evaluation

Tumor evaluation (chest, abdomen and pelvis) will be assessed at baseline by means of triphasic CT or MRI. CT scan is the preferred modality and should be used wherever possible. Measurable lesions -i.e., target lesions and the non-target lesions by which subsequent response assessments will be judged- must be identified during tumor assessment at baseline; the disease must be staged and progression confirmed at this time.

The tumor evaluation is to be repeated every 3 months or at EOS if reached earlier. During the extension period, tumor evaluation is recommended every 3 months

All images will be read locally at the site by the reviewer. Clinical decisions will be done locally by the investigator with the local radiologist.

All images will be saved on a CD-rom and locally stored at the site in order to allow any future double check of the tumor assessment, if needed.

Evaluation of the endpoints will be done by a local radiologist together with the investigator.

All patients with bone pain or bone uptake at Octreoscan guided imaging at baseline should repeat the assessment while on treatment (including MRI).

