7.2.1.2.2 Biochemical response rate (BRR)

The biochemical response rate (BRR) and biochemical progression will be evaluated on the basis of serum chromogranin A (CgA) levels.

Additionally, the biochemical response on the basis of urine 5-hydroxyindole acetic acid (5HIAA) will be assessed.

Response of CgA is defined as normalization or a $\geq 30\%$ reduction of serum CgA levels compared to baseline (Kouvaraki et al. 2004; Yao et al. 2010).

Response of 5HIAA is defined as normalization or a $\geq 50\%$ reduction of urinary 5HIAA levels compared to baseline (Bajetta et al. 1993; Bajetta et al. 2006).

Biochemical progression is defined as an increase of serum CgA levels $\geq 25\%$ vs. baseline (Bajetta et al. 1999; Brizzi et al. 2009).

CgA / 5HIAA

The serum parameter CgA and urine 5HIAA will be assessed for all patients at screening, on visits 8, 11, 14, 17 and at the end of core study visit/early withdrawn. In patients treated in the extension phase, serum and urine samples will be collected on visits 2, 4. In the course of the study, CgA and 5HIAA are collected at the same time points. In case of an unscheduled tumor evaluation, an additional blood and urine sample will be collected.

For CgA measurements in serum, 5.5 mL blood will be collected. For 5HIAA measurements, urine will be collected for 24 h. From this measurement, 10 mL urine will be analyzed. Serum and urine samples will be analyzed centrally.

It is worth underlining that some foods contain significant amounts of hydroxyindoles that may influence 5HIAA measurements. Thus, patients will be asked to amend their diet for three days before starting urine collection and during the collection to avoid interference with the test. Specifically, patients should avoid food containing high levels of indoles such as avocados, bananas, tomatoes, plums, walnuts, peanuts, almonds, pineapples, eggplants, and smoked fish. Patients will be also asked not to consume coffee, tea, alcohol, vanilla, chocolate, and tobacco for three days before and during urine collection.

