- PR = at least two determinations of PR or better at least 4 weeks apart before progression (and not qualifying for a CR) where confirmation required or one determination of PR prior to progression where confirmation not required
- SD = at least one SD assessment (or better) > 6 weeks after randomization/start of treatment (and not qualifying for CR or PR).
- PD = progression ≤ 12 weeks after randomization/ start of treatment (and not qualifying for CR, PR or SD).
- UNK = all other cases (i.e. not qualifying for confirmed CR or PR and without SD after more than 6 weeks or early progression within the first 12 weeks)

Overall lesion responses of CR must stay the same until progression sets in, with the exception of a UNK status. A patient who had a CR cannot subsequently have a lower status

other than a PD, e.g. PR or SD, as this would imply a progression based on one or more lesions reappearing, in which case the status would become a PD.

Once an overall lesion response of PR is observed (which may have to be a confirmed PR depending on the study) this assignment must stay the same or improve over time until progression sets in, with the exception of an UNK status. However, in studies where confirmation of response is required, if a patient has a single PR ($\geq 30\%$ reduction of tumor burden compared to baseline) at one assessment, followed by a $< 30\%$ reduction from baseline at the next assessment (but not $\geq 20\%$ increase from previous smallest sum), the objective status at that assessment should be SD. Once a confirmed PR was seen, the overall lesion response should be considered PR (or UNK) until progression is documented or the lesions totally disappear in which case a CR assignment is applicable. In studies where confirmation of response is not required after a single PR the overall lesion response should still be considered PR (or UNK) until progression is documented or the lesion totally disappears in which case a CR assignment is applicable.

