3.9 Assessment windows, baseline and post-baseline definitions, missing data handling

3.9.1 Assessment windows

Patients will be assessed at baseline (day -28 to -1) and will then attend up to 16 visits during the core study with a separate assessment being completed at the end of the core study (EOCS) (12 months), either completion or early withdrawal. Those patients presenting with clinical benefit and not experiencing unacceptable toxicity at the 12 month visit will continue into the extension phase until progression occurs. They will attend visits every 3 months with a separate assessment being completed at the end of the extension phase (EOEP) when progression occurs, patient withdraws or two years after treatment start of the last evaluable patient. All patients who discontinue study treatment must have safety evaluations 56 days after the last dose of pasireotide LAR or everolimus, whichever comes last. This includes those who didn't enter extension phase due to disease progression at week 52. Endpoints (i.e. EOCS and EOEP) will be summarized as per scheduled visits. Any data from unscheduled

visits (Unsch), will be listed. Early withdrawal visits will continue to be displayed at the EOCS visit i.e. it will not be re-mapped to the most appropriate visit.

Visits will be labeled as follows: Baseline, Day 1, Day 15, Day 21, Day 29, Day 49, Day 57, Day 85, Day 113, Day 141, Day 169, Day 197, Day 225, Day 253, Day 281, Day 309, Day 337, EOCS, 3 Mths Extn, 6 Mths Extn, 9 Mths Extn, 12 Mths Extn, 15 Mths Extn, ..., EOEP, Safety FU, Unsch.

The tumor assessments will be time-slotted using the time windows displayed in Table 2.

Table 2 - Time windows for tumor assessments

Time Window	Planned Visit Timing	Time Window Definition
Week 12	Study Day 85 (Week 12)]0; 126] days or]0; 18] weeks
Week 24	Study Day 169 (Week 24)]126; 210] days or]18; 30] weeks
Week 36	Study Day 253 (Week 36)]210; 294] days or]30; 42] weeks
Week 48	Study Day 337 (Week 48)]294; 351] days or]42; 50] weeks
Week 52	Study Day 365 (Week 52)]351; 379] days or]50; 54] weeks
Week 64	Study Day 449 (Week 64)]379; 491] days or]54; 70] weeks
Week k	Study Day x (Week y) x= k*7+1 ; y=k]x-43; x+41] days or]y-6; y+6] weeks

Study Day 1 = start of study treatment date

Similarly to tumor assessments, week-based time windows [REDACTED]. If more non-missing results fall into a specific time window, then the one will be chosen which is closer to the optimal study day of the specific time window.

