6.1 Implementation of RECIST

Tumor response and disease progression will be evaluated according to the Novartis guidelines based on RECIST 1.1 criteria (enclosed in protocol Appendix 1), unless otherwise noted.

The evaluation of overall lesion response at each assessment is a composite of the target lesion response, non-target lesion response and presence of new lesions as shown below. This information will be captured on the CRF.

Table 4 - Evaluation of overall lesion response

Target lesions	Non-target lesions	New Lesions	Overall lesion response
CR	CR	No	CR ¹
CR	Non-CR/Non PD	No	PR
CR, PR, SD	UNK	No	UNK
PR	Non-PD and not UNK	No	PR ¹
SD	Non-PD and not UNK	No	SD ^{1,2}
UNK	Non-PD or UNK	No	UNK ¹
PD	Any	Yes or No	PD
Any	PD	Yes or No	PD
Any	Any	Yes	PD

¹ This overall lesion response also applies when there are no non target lesions identified at baseline.
² Once confirmed PR was achieved, all these assessment are considered PR.

A listing of the tumor assessments and responses will be presented for the full analysis set after completion of core phase and extension phase analyses. This will include evaluation number, type of lesion (target, non-target, new), overall assessment, number, location, measurement method, evaluation date, longest diameter (cm), lesion status and an overall lesion response as per the investigator. Patients who discontinue study treatment after 12 months of treatment without evidence of progression or for reasons other than disease progression will continue to have tumor evaluation assessments unless consent is withdrawn. These will be flagged in this listing.

Another listing of lesion locations and descriptions will also be produced for the full analysis set. This will include the evaluation number, the type of lesion (target, non-target, new), the

number, the evaluation date, the location, the description, the measurement method and the measurement method detail.

For each time to event assessment, the assessment date is calculated as follows:

- the latest of all measurement dates for assessment with overall lesion response = CR, PR, SD or UNK.
- the earliest of all measurement dates for assessments with overall lesion response = PD.

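### SAP 7.5 waives the 6-week minimum for stable disease on a premise that holds only for scheduled scans, so an early-withdrawal scan can count as disease control

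*SAP*

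**What the plan says.** Protocol Appendix 14.1.3.1 sets a time condition: "SD = at least one SD assessment (or better) > 6 weeks after randomization/start of treatment". A patient who does not meet it, and who has neither a confirmed response nor early progression, is UNK. The appendix describes that residual class as "not qualifying for confirmed CR or PR and without SD after more than 6 weeks or early progression within the first 12 weeks".

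SAP 6.1 adopts the appendix, "according to the Novartis guidelines based on RECIST 1.1 criteria (enclosed in protocol Appendix 1), unless otherwise noted". SAP 7.5 then notes otherwise for SD: "there is no specific time needed from baseline as the first tumor evaluation takes place after 12 weeks". It ties that first evaluation to Visit 8 and concludes that the 6-week minimum is met anyway. SAP 7.2 builds the disease control rate on best overall response of CR, PR or SD during the core study, in the full analysis set. SAP 7.5 is the only place where the SAP says when SD qualifies as best overall response.

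On scan timing, protocol 7.2.1.1.1 says: "The tumor evaluation is to be repeated every 3 months or at EOS if reached earlier". Protocol 7.1.4 has patients who stop treatment seen as soon as possible, "at which time all of the assessments listed for the end of core study visit/early withdrawn will be performed", and Table 7-1 marks tumour evaluation at that visit. Protocol 7.2.1.2.2 provides for unscheduled scans: "In case of an unscheduled tumor evaluation, an additional blood and urine sample will be collected". The Week 12 row of SAP Table 2 (section 3.9.1) runs over "0; 126] days or]0; 18] weeks", so it opens at day 0.

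**The concern.** The SAP does not reject the 6-week rule. It assumes that the rule can never bind. If a scan can be done and read before 6 weeks, the assumption fails, and the SAP and the protocol give the same patient different best overall responses.

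The difference matters because a lesion unchanged a few weeks after first dose says little about treatment effect. Under the SAP wording, a patient who leaves early with one unchanged scan is a success for disease control. Under the protocol's appendix the same patient is not a success but can stay in the denominator. The reported disease control rate would then depart from the protocol's own definition, and in one direction only, upwards.

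**Working it through.** The plan attaches no figure to this rule, so the check is of the timing premise, then the classification, then the size.

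**1. Is 12 weeks right for the scheduled scan?** Yes. Visit 8 is Day 85 = 12 × 7 + 1.

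**2. Does the SAP's windowing keep earlier scans out?** No. The general row of Table 2 has x = 7k + 1 and a window of ]x − 43; x + 41]. At k = 12, x = 85, which gives ]42; 126], a lower bound at about 6 weeks. The explicit Week 12 row opens at 0 instead. A scan on Day 20, for example, is slotted as Week 12.

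**3. Does anything else in the derivation exclude it?** Not that I can find. SAP 6.2 derives tumour endpoints from the sequence of overall lesion responses at each assessment. SAP 7.5 runs best overall response from start of treatment to progression, death or withdrawal of consent, not to end of treatment. The appendix default drops only scans more than 30 days after the last dose.

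**4. Classification side by side**

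| Patient | Appendix 14.1.3.1 | SAP 7.5 | Disease control under SAP 7.2 |
|---|---|---|---|
| Stops on Day 20, one scan, SD | UNK | SD | Yes |
| First scan on Day 85, SD | SD | SD | Yes |
| Early unscheduled SD scan, PD by week 12 | PD | SD, unless the window rule replaces the early scan | Possibly |
| Stops early, no scan or UNK scan | UNK | Not SD | No |

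The first row is the clear conflict. The third depends on how SAP 3.9.1 treats several results in one window.

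**5. Which endpoints are touched?**
- Month 9 progression-free rate: no. Protocol 10.4.3 and SAP 6.3.1 count anyone who discontinues before the 9-month assessment as not progression-free.
- Objective response rate: no. SAP 7.5 requires CR or PR to be confirmed at least 4 weeks later.
- Disease control rate (SAP 7.2) and the best overall response frequencies (SAP 7.5): yes.

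**6. Size.** The Amendment 5 rationale gives 41, 42 and 41 patients per arm. The overstatement for m misclassified patients is m/n:
- n = 41: 1/41 = 2.4, 2/41 = 4.9, 4/41 = 9.8 points
- n = 42: 1/42 = 2.4, 2/42 = 4.8, 4/42 = 9.5 points

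The value of m is not in the documents. Over an assumed range of 0 to 4 per arm, the overstatement is 0 to 9.8 points.

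As an illustration, take an assumed 25 of 41 with disease control under the appendix rule, with exact 95% intervals:
- m = 0: 25/41 = 61.0% (44.5 to 75.8)
- m = 1: 26/41 = 63.4% (46.9 to 77.9)
- m = 2: 27/41 = 65.9% (49.4 to 79.9)
- m = 4: 29/41 = 70.7% (54.5 to 83.9)

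**The case against.** **Early scans may be rare.** Protocol 7.2.2.6.4, repeated in SAP 10.10, says that after discontinuation an end-of-study MRI/CT is needed only if that visit falls 3 months or more after the previous one. Baseline imaging may be up to 28 days before treatment (protocol 7.2.1.1.4), so a patient leaving on Day 20 is well inside 3 months. Sites following that text could skip the scan, leaving no SD to count. This stands as a reason to expect fewer cases. It does not remove the problem: the text sits in the gallbladder section, conflicts with protocol 7.2.1.1.1 and Table 7-1, and does not exclude a scan that was done.

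**The SAP may discard unscheduled scans.** SAP 3.9.1 says unscheduled-visit data are listed, and that the result closest to the planned day is chosen when several fall in one window. The adjoining sentence is partly redacted, so it is unclear whether the second rule covers tumour scans. If it does, an early SD scan followed by a Day 85 scan is superseded. That does not help when the early scan is the only one.

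**The reach is narrow.** Disease control is a secondary rate, estimated per arm with an exact interval and no planned between-arm test. This is correct and limits the weight of the point.

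Three stronger readings are tempting, and the documents do not support them:
- A reader might infer that early-withdrawal scans were common because only 43 of 124 patients completed the core phase. The 81 others left over 12 months, and the Amendment 5 rationale gives neither reasons nor timing. The number with an SD-only scan within 6 weeks could be zero.
- A reader might infer that the arm with most early toxicity withdrawals gains most. That requires an early scan read as SD; a patient with no scan, or an UNK reading, adds nothing.
- A reader might infer that the primary endpoint is inflated, since protocol 3.1 also labels it disease control rate and defines that by best overall response. Protocol 10.4.3 and SAP 6.3.1 derive it from the Month 9 evaluation and count early leavers as failures.

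**Conclusion.** The point holds in limited form. The waiver rests on a premise that is true of scheduled scans but not of all the scans the protocol calls for or foresees. As written, the SAP can class a patient as SD, and so as disease control, whom the protocol's appendix classes as UNK. The contradiction is a matter of text and needs no assumption.

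The size does need one. It is about 2.4 points per affected patient in an arm of 41 or 42, hence 0 to 9.8 points for an assumed 0 to 4 patients per arm. If the sponsor's premise proved right in the data, restoring the rule would change no result. The change should still be made, because it is cheap and brings a named secondary endpoint back to the protocol's definition.

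**What to change.** - Delete the waiver in SAP 7.5 and apply the appendix rule there and in SAP 7.2: SD as best overall response requires an SD or better assessment more than 6 weeks (more than 42 days) after start of treatment. Patients with SD only at or before that time are UNK and stay in the full analysis set denominator. State the day count: with first dose as Day 1, more than 42 days after start means Study Day 44 or later (42 + 1 = 43 is excluded).
- Check the core-phase disease control and best overall response tables against this rule, and re-tabulate if any patient changes class. The core analysis was run in February 2016, and neither SAP 7.2 nor SAP 3.4.2 provides for repeating disease control after the extension, so editing the SAP alone would not correct a reported figure.
- Reconcile protocol 7.2.2.6.4 and SAP 10.10 with protocol 7.2.1.1.1 and Table 7-1 on whether imaging is expected at early withdrawal.

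The cost is one SAP sentence, one date condition in the derivation and possibly a re-run of the core tables. The disease control rate may come out slightly lower.

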7.6 Biochemical Response Rate

The endpoint of BRR is defined as the percentage of patients showing normalization, i.e. return to within normal ranges, or a decrease of $\geq 30\%$ from baseline of serum Chromogranin A (CgA) concentrations compared to baseline. The parameter of biochemical response will be summarized by arm with frequency counts, percentages and 95% exact confidence intervals. Additionally, the biochemical response on the basis of urine 5-hydroxyindole acetic acid (5HIAA) will be assessed, with a response being defined as normalization or a $\geq 50\%$ reduction of 5HIAA levels from baseline.

Patients who are within normal range at baseline will be excluded from the tables. The endpoint of BRR will be analyzed based on core phase data only.

Absolute and relative changes from baseline for each of CgA and 5-HIAA will be summarized by arm for the full analysis set up to Visit 4 of extension phase. Any data collected after Visit 4 of extension phase will not be summarized or listed in the CSR.

A listing containing the CgA and 5-HIAA results will be presented along with the visit, sample date, analyte name (CgA, 5-HIAA) and analyte nature/type (DNA, RNA, Protein).

[figure not shown]
7.7 Duration of Biochemical Response

[figure not shown]
[figure not shown]
Duration of biochemical response (DBR) is defined as the time from the first documentation of biochemical response during core phase to the first documentation of biochemical progression or death due to any cause, whichever occurs first (including extension phase data, if applicable at the time of the extension phase analyses). Biochemical progression is defined as an increase of serum CgA levels $\geq 25\%$ compared to baseline. DBR data will be censored on the date of the last CgA assessment on study for patients who do not have biochemical progression and who do not die due to any cause while on study. DBR will be summarized for the subset of patients from the full analysis set who had biochemical response, patients with CgA levels within normal range at baseline will also be excluded from the table. This will be explored using the Kaplan-Meier method, graphically presenting the Kaplan-Meier curve and also tabulating the number with the event, the number censored and the estimators along with 95 percent confidence intervals. The analysis of this endpoint will be repeated based on cumulative study data at the time of extension phase analyses.

[figure not shown]
7.8 Biochemical Progression-free Survival (BPFS)

[figure not shown]
[figure not shown]
Biochemical progression free survival (BPFS) is the time from the first study drug administration to the first documentation of biochemical progression or to death due to any cause, whichever occurs first (including extension phase data, if applicable at the time of the extension phase analyses). Biochemical progression is defined as an increase of serum CgA levels $\geq 25\%$ versus baseline. BPFS data will be censored on the date of the last CgA assessment on study for patients who do not have biochemical progression and who do not die due to any cause while on study. BPFS will be analyzed in the FAS set by presenting the Kaplan-Meier curve and estimators. The table used will be similar to that described for PFS.

[figure not shown]
The analysis of this endpoint will be repeated based on cumulative study data at the time of extension phase analyses.

[figure not shown]

[figure not shown]

[figure not shown]

10 Safety evaluation

For all safety analyses, the safety set will be used. All safety analyses and listings will be rerun after completion of the extension phase based on cumulative study data from both core and extension phases. The assessment of safety will be based primarily on the frequency of AEs and laboratory abnormalities. Other safety data (e.g. gallbladder assessments) will be summarized appropriately.

The overall observation period will be divided into three mutually exclusive segments:

1. Pre-treatment period: from day of patient's informed consent to the day before first dose of study medication

2. On-treatment period: from day of first dose of study medication to 56 days after last dose of study medication

3. Post-treatment period: starting at day 56+1 after last dose of study medication.

The listings will all contain a flag to identify which period the event occurred in.

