4.3 Definition of end of the study

The end of the study is defined as when all patients have discontinued the study.

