Visit No.	Category	Reference to Section 7.2	Extension phase					End of extension phase /Early withdrawn	Safety FU visit**
			1	2	3	4	Every 3 mos		
Month of extension phase			3	6	9	12	Every 3 mos		
Coagulation (INR)	D	7.2.2.5.2	X	X	X	X	X	X	
CgA and 5HIAA****	D	7.2.1.2		X		X			
Urinalysis	D	7.2.2.5.8	X	X	X	X	X	X	
Serum lipid profile	D	7.2.2.5.6	X	X	X	X	X	X	
Pregnancy test	D	7.2.2.5.9	X	X	X	X	X	X	
Monitoring of HBV-DNA, HCV RNA-PCR (if applicable)	D		Every 4 weeks as indicated in Section 6.1.4.8						
Anti-HAV, IgM, HbsAg, Anti-HBc, anti-HCV (if positive, PCR viral load should be assessed), Anti-HEV, ANA antibodies, anti-smooth muscle antibodies, CMV and EBV	D		If LFTs meet criteria reported in Section 6.1.5						
Pasireotide LAR injections (q28d)	D		Every 28 days from V18 of Core phase						
Everolimus administration (daily)	D		Daily from V18 of Core phase						
Adverse events	D		X	X	X	X	X	X	X
Concomitant medications	D		X	X	X	X	X	X	X
Study completion	D							X	

*Only for patients treated with pasireotide LAR

**The safety follow up visit should be performed 56 days after the last dose of pasireotide LAR or everolimus, whichever comes last.

*** Patients who discontinue study treatment after 12 months of treatment without evidence of progression or for reasons other than disease progression will continue to have tumor evaluation assessments until disease progression or last patient last visit (LPLV) whichever occurs first.

**** CgA and 5HIAA will only be collected until extension visit 4.

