Biochemical response (BR) is defined in [Section 7.2.1.2](#). BR rate (BRR) is the percentage of patients showing a $\geq 30\%$ decrease or normalization of serum CgA levels compared to baseline. Additionally, parameters of biochemical response as well as absolute and relative changes from baseline in these parameters will be descriptively summarized.

Additionally, the biochemical response on the basis of urine 5-hydroxyindole acetic acid (5HIAA) will be assessed, with a response being defined as normalization or a $\geq 50\%$ reduction of 5HIAA levels from baseline

Duration of biochemical response (DBR) is defined as the time from the first documentation of biochemical response to the first documentation of biochemical progression or to death due to any cause, whichever occurs first. Biochemical progression is defined as an increase of serum CgA levels $\geq 25\%$ *versus* baseline. DBR data will be censored on the date of the last tumor marker assessment on study for subjects who do not have biochemical progression and who do not die due to any cause while on study.

Biochemical progression free survival (BPFS) is the time from first study drug administration to the first documentation of biochemical progression or to death due to any cause, whichever occurs first. BPFS data will be censored on the date of the last tumor marker assessment on study for subjects who do not have biochemical progression and who do not die due to any cause while on study.

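### In the exploratory extension rerun of BPFS, deaths count without time limit but survivors are censored at a CgA that stops at about month 24, so one late death takes an arm's curve to 0

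*SAP*

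**What the plan says.** SAP 7.8 defines BPFS as time from first dose to biochemical progression or death from any cause, extension data included. On censoring it says "BPFS data will be censored on the date of the last CgA assessment on study for patients who do not have biochemical progression". The same sentence exempts anyone whose death falls within the study; such a patient has an event on the date of death. Nothing limits the gap between the last CgA and a death that counts. SAP 7.8 adds: "The analysis of this endpoint will be repeated based on cumulative study data at the time of extension phase analyses".

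SAP 7.7 has the matching rule for DBR: "DBR data will be censored on the date of the last CgA assessment on study for patients who do not have biochemical progression". Both follow protocol 10.5.2: "BPFS data will be censored on the date of the last tumor marker assessment on study for subjects who do not have biochemical progression".

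Two other provisions fix the time scale. The footnote to protocol Table 7-2 reads "CgA and 5HIAA will only be collected until extension visit 4", and Visit 4 is month 12 of the extension, so about month 24 from the start of treatment. SAP 7.6 adds, for CgA and 5-HIAA: "Any data collected after Visit 4 of extension phase will not be summarized or listed in the CSR". Protocol 4.3 sets no calendar limit: "The end of the study is defined as when all patients have discontinued the study". SAP 3.4.2 places the extension analysis after the last patient stops study treatment.

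**The concern.** An event-free patient leaves the risk set at the last CgA if alive, but stays in it until death if the patient dies on study later. Who is at risk at a given time therefore depends on what happens afterwards. While CgA is still being measured the gap is short. After Visit 4 it has no limit, and the risk set contains only patients who are going to die.

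This reaches reported figures. SAP 7.8 says the BPFS table will resemble the PFS table, and SAP 7.1 puts the median and the 25% and 75% percentiles in that table. An arm could be shown with BPFS of 0% while patients without biochemical progression are still alive, and a percentile could be read off the date of one death.

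**Working it through.** The documents give no expected BPFS, event count or power for this endpoint, so there is no figure of the plan to reproduce. The check applies the product-limit formula, S(t) = product of (1 - d/n), to the SAP's event and censoring rules. The arms below are assumed, because arm-level CgA data are not in the documents.

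**1. The general result.** After every survivor's last CgA, one later death has d = 1 and n = 1. S is multiplied by 1 - 1/1 = 0, whatever its value at month 24.

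**2. A worked arm of 41.** Assumed biochemical progressions: 4, 3, 2, 1, 1 at months 3, 6, 9, 12, 18. Assumed censorings at the same months: 8, 6, 5, 2, 3. The numbers at risk are 41, 29, 20, 13 and 10, and 6 are left at month 24.

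- S24 = 37/41 x 26/29 x 18/20 x 12/13 x 9/10 = 0.605.
- One death at month 36, rule as written: 0.605 x (1 - 1/1) = 0. The median and the 75% percentile both become 36 months.
- Same death, the other five kept at risk: 0.605 x 5/6 = 0.504. The median is not reached.
- Deaths counted only up to Visit 4: the curve ends at 0.605. The median is not reached.

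**3. Other month-24 levels.** Three further assumed arms of 41, with one death at month 30:

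| S24 | As written | Survivors kept at risk | Capped at Visit 4 | Median as written / capped |
|---|---|---|---|---|
| 0.624 | 0 | 0.520 (n = 6) | 0.624 | month 30 / not reached |
| 0.447 | 0 | 0.372 (n = 6) | 0.447 | month 18 / month 18 |
| 0.306 | 0 | 0.230 (n = 4) | 0.306 | month 9 / month 9 |

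The median moves only where S24 is above 50%. S24 is above 25% in all three arms, so the 75% percentile is set by the late death each time. With two late deaths, at months 30 and 36, the first arm goes from 0.624 to 0.312 to 0.

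**4. Size in general.** With n patients event-free at the time of the death, the comparison is 0 against S24 x (n - 1)/n. For assumed S24 of 30 to 70% and n of 2 to 8, this runs from 0.30 x 1/2 = 15% to 0.70 x 7/8 = 61%.

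**5. DBR.** Time runs from onset of response, so a late death need not be the longest time. Take five responders, four of them censored at 21, 18, 15 and 12 months, and one who dies at month 30. If that response began at month 12, DBR is 18 months, three are at risk and S = 2/3 = 0.667. If it began at month 3, DBR is 27 months, one is at risk and S = 0.

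**The case against.** The SAP carries out protocol 10.5.2 faithfully, and SAP 3.4 calls the extension analysis exploratory. Both are true. The first means that this is a weakness in the rule, not a departure from the protocol; the second limits its weight.

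A reader might infer that the SAP breaks the sponsor's own convention. By default, Table 14-5 in protocol Appendix 1 (situation C2) censors a death after two or more missed assessments at the last adequate one. But that table covers PFS, time to progression and duration of response. It shows that the sponsor knows the problem; it does not bind a CgA endpoint.

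No frequency can be given. The documents do not report deaths after Visit 4 in patients without biochemical progression, and any rate would rest on outside assumptions. At Amendment 5, 11 patients in all three arms together were still in the extension. It is also unclear whether a death after stopping treatment is on study: protocol 6.3.2 treats patients who stop study drug as withdrawn after the final visit, while protocol 7.1.5 continues their scans.

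Numbers at risk under the plot, which SAP 7.1 specifies for PFS, would reveal a last step based on one patient if they were also used for BPFS. They would not correct the tabulated percentiles.

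Finally, SAP 3.4.2 says that only PFS and safety are repeated after the extension. If that prevailed there would be no BPFS rerun. SAP 7.7 and 7.8 are more specific, however, and the SAP change log for Amendment 2.0 records both reruns, so the rerun is the better reading. Nor does the two-year study end still in SAP 1 remove the problem: patients randomized before the last one can be followed past their own month 24.

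**Conclusion.** The concern holds for the extension rerun of BPFS. One on-study death, in a patient without earlier biochemical progression and later than every survivor's last CgA in that arm, takes the curve to 0. It also sets any percentile not already reached: the 75% percentile if month-24 BPFS is above 25%, and the median only if it is above 50%. If no such death occurs there is no effect.

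Three stronger readings are tempting and not supported. DBR does not necessarily fall to 0; it can be distorted in the same direction, but the result depends on when response began. The median is not generally wrong; in two of the three arms tabulated it does not move. The trial's main results are not touched: the primary endpoint, core-phase BPFS and DBR, the 3- to 12-month estimates and radiological PFS do not depend on this rule after Visit 4.

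The fall to 0 follows from the stated rules alone. The sizes shown rest on assumed arms. The rule should be changed, because it can give a wrong estimate for a secondary endpoint and the change is small.

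**What to change.** In SAP 7.7 and 7.8, for the extension-phase rerun only, state that a death is an event only if it occurs on or before the planned date of extension Visit 4, and that otherwise a patient without biochemical progression is censored at the last CgA assessment. List this in SAP 2 as a difference from protocol 10.5.2; protocol Appendix 14.1.4.1 allows deviations to be defined in the RAP.

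A missed-assessment rule modelled on C2 is not advised here. CgA is taken every 3 months in the core but only at Visits 2 and 4 of the extension, so one missed sample would mean different gaps. Applied generally, it would also change the rule for the core analysis, already run in February 2016.

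Add BPFS and DBR to the repeated analyses in SAP 3.4.2. As an editorial matter, replace the two-year study end in SAP 1 with the protocol 4.3 definition and delete the two-year clause in SAP 3.9.1.

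The cost is one derivation rule for two endpoints and text edits, with no new data, visits or protocol amendment. The downside is that deaths after Visit 4 no longer contribute to BPFS or DBR. They are still reported in the safety and PFS analyses, under the rules of those analyses.
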